10.8. Appendix 8: Protocol Amendment History

The Protocol Amendment Summary of Changes Table for the current amendment is located directly before the Table of Contents (TOC).

Amendment (a)

Overall Rationale for the Amendment:

This amendment incorporates changes requested by regulatory agencies. In addition, this amendment includes changes made to correct and clarify information for sites.

Section # and Name	Description of Change	Brief Rationale
Section 1.1. Synopsis	Replaced “anti-PD-1/L1” with “Pembrolizumab”; Added in pembrolizumab dose	Based on FDA feedback
Section 1.2.1. Phase 1a: Dose Escalation Schema	Replaced “PD-1/L1 Combination” with “Pembrolizumab” for Part B of the study schema	Based on FDA feedback
Section 1.3. Schedule of Activities	Changed “Single local ECG” to “Central triplicate ECGs” for on-treatment activities	Updated to be in line with common Lilly practice
Section 1.3. Schedule of Activities	Addition of plasma and stool sample collection information	Clarification
Section 1.3. Schedule of Activities	Addition of “Pregnancy Test” to Post-Treatment Schedule of Activities	Based on pembrolizumab specific language
Section 1.3. Schedule of Activities	Changed “PBMC” to “Whole Blood for Flow Profile”	Clarification
Section 2.3. Benefit/Risk Assessment	Addition of language regarding pembrolizumab benefit/risk information	Based on FDA feedback
Section 4.1.1.2. Dose-Limiting Toxicity Determination	DLT table modified	Based on FDA feedback
Section 4.1.1.4. Determination of Recommended	Addition of text regarding the use of data in the 90-day follow-up period.	Based on FDA feedback

Section # and Name	Description of Change	Brief Rationale
Phase 2 Dose		
Section 4.3. Justification for Dose	Addition of language regarding dose of pembrolizumab in parts B and D of the study.	Based on FDA feedback
Section 5.1. Inclusion Criteria	Modification of inclusion criteria [2] and [8]	Based on FDA feedback
Section 6.1. Study Intervention(s) Administered	Replaced “anti-PD-1/L1” with “Pembrolizumab”; Added in footnote regarding combination dose levels	Based on FDA feedback
Section 6.6. Dose Modification	Addition of language regarding dose delays and omissions	Based on FDA feedback
Section 6.6.2. Dose Modifications of Pembrolizumab	Addition of language regarding dose modifications for pembrolizumab	Based on FDA feedback

4.1. Primary Objective

- **Phase 1a Dose Escalation (Part A & Part B):** to assess the safety and tolerability of LY3435151, thereby identifying the recommended Phase 2 dose (RP2D), administered as monotherapy and in combination with pembrolizumab, in patients with advanced solid tumors of the following types: triple-negative breast cancer (TNBC), gastric adenocarcinoma (GC), head and neck squamous cell carcinoma (HNSCC), squamous cervical carcinoma, high-grade serous ovarian carcinoma, hepatocellular carcinoma (HCC), undifferentiated pleomorphic sarcoma (UPS), and leiomyosarcoma (LMS).
- **Phase 1b Dose Expansion (Part C & Part D):** to assess the safety and tolerability of LY3435151:
 - administered as monotherapy (Part C), all patients must be programmed death-1 (PD-1) /programmed death-ligand 1 (PD-L1) antagonist naïve:
 - C1: TNBC (not eligible for atezolizumab-containing therapies)
 - C2: GC (including gastroesophageal junction)
 - administered in combination with pembrolizumab (Part D), all patients must be PD-1/PD-L1 antagonist naïve:
 - D1: TNBC (not eligible for atezolizumab-containing therapies)
 - D2: GC (including gastroesophageal junction)
 - D3: tumor-infiltrating lymphocyte (TIL)-selected cohort with the following tumor types: HNSCC, squamous cervical carcinoma, high-grade serous ovarian carcinoma, HCC, UPS, and LMS

4.2. Secondary Objectives

- to assess the pharmacokinetics (PK) of LY3435151, administered as monotherapy and in combination with pembrolizumab, in patients with solid tumors
- to document any antitumor activity per Response Evaluation Criteria in Solid Tumors (RECIST) v1.1 observed with LY3435151, when administered as monotherapy or in combination with pembrolizumab, in patients with solid tumors

4.3. Exploratory Objectives

- to assess the relationship between biomarkers, dose/exposure, and clinical outcomes, particularly in relation to tumor TIL levels
- to document survival status observed with LY3435151 when administered as monotherapy or in combination with pembrolizumab to patients with solid tumors associated with TIL positivity

- to document antitumor activity based on immuno-RECIST (iRECIST) observed with LY3435151 when administered as monotherapy or in combination with pembrolizumab to patients with solid tumors associated with high TIL positivity

5. A Priori Statistical Methods

5.1. Summary of Study Design

Study JZIA is a Phase 1a/1b, multicenter, open-label dose-escalation study followed by a randomized dose-expansion study of LY3435151 as monotherapy and in combination with pembrolizumab in patients with advanced solid tumors.

5.1.1. Dose Escalation Phase

Phase 1a (dose escalation) will assess the safety and tolerability of LY3435151 to identify a monotherapy RP2D and a combination RP2D in patients with solid tumors associated with TIL positivity:

- TNBC
- GC (including gastroesophageal junction)
- HNSCC
- squamous cervical carcinoma
- high-grade serous ovarian carcinoma
- HCC
- UPS and LMS

Patients enrolled in Part A (Cohorts A1 through A6) will receive LY3435151 monotherapy. Patients enrolled in Part B (Cohorts B1 and B2) will receive LY3435151 and pembrolizumab.

The RP2D will be determined based on the number of observed dose-limiting toxicities (DLTs) and PK/pharmacodynamic (PD) data, and may be below the maximum tolerated dose (MTD), which may not necessarily be reached during the dose escalations. The dose-escalation phase will employ a modified toxicity probability interval-2 (mTPI-2) method and, starting with Cohort A2, will enroll at least 3 evaluable patients per cohort. Treatment cycles will consist of 21 days. A 2-cycle DLT observation period (42 days) will apply to all cohorts in Phase 1a.

[figure not shown]
One patient will be enrolled in Cohort A1 and will receive a 10-mg dose on Cycle 1 Day 1. If the 10-mg dose level DLT period is cleared, Cohort A2 (30-mg dose level) will be initiated. If the patient in Cohort A1 experiences a DLT, additional patients will be enrolled into Cohort A1 following the mTPI-2 method. Based on the mTPI-2 method, at least 4 additional patients will need to be enrolled and experience no DLTs during the DLT observing period before escalating to the next dose level (Cohort A2).

After the first patient in Cohort A2 receives the first dose of LY3435151, there will be a delay of 1 week before the second patient receives LY3435151 to allow for safety observation. In all subsequent cohorts, the first patient in each dose level will be observed for at least 24 hours before treatment of additional patients; no additional delays are required for subsequent patients.

Patients in Cohorts A2, A3, A4, A5, and A6 will receive proposed doses of 30 mg, 100 mg, 300 mg, 900 mg, and 1800 mg, respectively, provided safety is established in the preceding cohorts. Once the DLT period of 42 days for every 3 weeks (Q3W) is completed for respective dose levels within Cohorts A1 to A6, 2 selected cohorts can be expanded with an additional 6 patients each to further inform safety, PK, and PD. For example, additional patients at Dose Level 5 (900 mg Q3W) may be enrolled in parallel with Cohort A6 after Cohort A5 has cleared the DLT period.

In the Combination Dose Escalation Period (Part B), 2 dose levels will be explored. Dose Level 1 in Part B will be decided based on, but not limited to, the safety and PK/PD data from monotherapy expansion cohorts. The dose of pembrolizumab will remain constant. Once enrollment to Dose Level 1 in Part B begins, dose escalation will occur in parallel for both Part A and Part B. However, enrollment in a Part B cohort can begin only after all previous dose level cohorts in monotherapy and combination dose escalation (as applicable) are complete, as determined by Eli Lilly and Company (Lilly). For example, if Dose Level 5, 900 mg Q3W, is decided as the starting dose level for Part B, Cohort B1 will only begin after the safety of Dose Level 5 in monotherapy dose escalation is cleared, and Cohort B2 may begin only after both Cohort A6 and Cohort B1 are complete.

If safety data from Part A indicate that de-escalation of the LY3435151 dose is warranted, no additional patients will be enrolled in Part A or Part B at dose levels higher than the de-escalated dose.

Abbreviations: n = number of participants; RP2Dc = combination recommended Phase 2 dose; RP2Dm = monotherapy recommended Phase 2 dose; TBD = to be determined.

^a May include backfill participants.

^b Refer to Section 5.8 of Interim Analyses.

^c LY3435151 dosing in combination will begin 1 dose level below the tolerated monotherapy dose level.

[figure not shown]
Figure JZIA.1. JZIA Study Design Scheme – Dose Escalation

5.1.2. Dose Expansion Phase

For both Part A and Part B, after all patients in the dose escalation phase have completed the DLT observation period or discontinued, an interim safety and PK/PD analysis will be conducted before opening the dose expansions. That is, the randomized Dose Expansion Cohort will begin after the completion of both Dose Escalation Part A and Dose Escalation Part B.

In Dose Expansion Phase 1b, a 2-stage design with randomization will be implemented to determine the treatment for patients with immuno-oncology (IO) naïve TNBC and GC. Within each tumor type of IO-naïve TNBC and GC in the dose expansion phase, Stage 1 will enroll 16 patients to be randomized with 1:1 ratio to receive either LY3435151 monotherapy (Cohort C1 or C2) or LY3435151 and pembrolizumab combination therapy (Cohort D1 or D2). At Stage 2, approximately 32 additional patients in each tumor type will be enrolled to receive LY3435151 in combination with pembrolizumab (Cohort D1 or D2). An interim data review will be performed based on safety, efficacy, and PK/PD data from the first 20 enrolled patients in the combination dose expansion (including 8 patients from Stage 1 and the first 12 patients from Stage 2) for each of the 2 tumor types of IO-naïve TNBC and GC. When the interim analysis in Stage 2 is performed for each tumor type, enrollment might still continue to enroll additional 20 patients, unless the totality of evidence suggests otherwise.

Approximately 30 patients with other IO-naïve tumor types will be selected for enrollment based on TIL positivity and will receive LY3435151 in combination with pembrolizumab (Cohort D3).

Abbreviations: GC = gastric adenocarcinoma; n = number of participants; R = randomization; RP2Dc = combination recommended Phase 2 dose; RP2Dm = monotherapy recommended Phase 2 dose; TIL = tumor-infiltrating lymphocyte; TNBC = triple-negative breast cancer.
^a Refer to Section 5.8 of Interim Analyses.

Figure JZIA.2. JZIA Study Design Schema – Dose Expansion

5.2. Determination of Sample Size

5.2.1. Statistical Hypotheses

In the dose escalation phase (Part A and Part B), the hypothesis is that there is a tolerable dose level for LY3435151 in both monotherapy and in combination with pembrolizumab.

In the dose expansion phase (Part C and Part D), the objective is to evaluate the safety and tolerability, as well as preliminary antitumor activity, of LY3435151 in both monotherapy and in combination with pembrolizumab in the prespecified tumor types. No formal hypothesis testing will be performed to demonstrate any statistically significant improvement in objective response rate. Therefore, specification of alternative hypotheses on the overall response rate (ORR) does not apply.

5.2.2. Sample Size Determination

The primary objective of this study is to assess the safety and tolerability of LY3435151, thereby identifying and confirming the RP2D of LY3435151, to be administered as monotherapy and in combination with pembrolizumab, in patients with solid tumors associated with high TIL

positivity. The secondary objective is to evaluate PK and any observed evidence of clinical efficacy.

With at least 3 patients treated at the RP2D in the dose escalation phase and additional patients treated at the RP2D in the dose expansion phase, a total of at least 20 patients can provide adequate precision for the estimated incidence rate of the following quantities of interest:

- (1) patients having a specified AE, or
- (2) patients showing a response (partial response [PR]/complete response[CR]) to treatment

In the dose expansion phase for both TNBC and GC, approximately 16 patients in each of these 2 tumor types will be randomized with a 1:1 ratio to receive LY3435151 as monotherapy or in combination with pembrolizumab (Stage 1). The sample size of $n=16$ in each tumor type is determined in order to minimize the patients receiving monotherapy but still provide sufficient precision to evaluate the PK/PD and safety data between monotherapy and combination therapy. Following the randomization stage, approximately 32 additional patients in each of the 2 tumor types will be enrolled to receive LY3435151 in combination with pembrolizumab (Stage 2). At each interim analysis for TNBC and GC, clinical data from approximately 20 patients in the combination dose expansion (8 from Stage 1 and 12 from Stage 2) will be available to evaluate the antitumor activity of the combination therapy. If the interim results suggest continuation of enrollment for the evaluated tumor type in TNBC and GC, an additional 20 patients will be enrolled to receive combination therapy in Stage 2 in the corresponding tumor type. Therefore, a total of approximately 40 patients will be enrolled in each tumor type for the evaluation of antitumor activity of combination therapy.

In the dose expansion phase for other tumor types associated with TIL positivity, the sample size of $n=30$ in combination therapy provides data to evaluate the safety and PK/PD profile. The sample size of $n=30$ also allows to potentially assess the antitumor activity of LY3435151 in combination with pembrolizumab in tumor types other than TNBC and GC.

With a total sample size of $n=20$ or $n=40$, example point estimates of incidence rates and corresponding 2-sided 95% confidence intervals (CIs) are summarized in the table below. The values are provided as a reference for estimation rather than a basis of any decision criteria. The RP2D may be revised based on the safety data obtained in the dose expansion phase (Iasonos and O'Quigley 2013).

Table JZIA.5.1. Estimated Incidence Rate and 2-Sided 95% Confidence Interval

Number of Cases	Estimated Rate	n=20		Number of Cases	Estimated Rate	n=40	
		95% CI ^a				95% CI ^a	
		Lower Limit	Upper Limit			Lower Limit	Upper Limit
0	0.0	0.0	0.17	0	0.0	0.0	0.09
3	0.15	0.03	0.38	5	0.13	0.04	0.27
5	0.25	0.09	0.49	10	0.25	0.13	0.41
10	0.50	0.27	0.73	15	0.38	0.23	0.54
15	0.75	0.51	0.91	20	0.50	0.34	0.66

Abbreviations: CI = confidence interval; n = number of participants.

^a 95% Clopper-Pearson interval for binomial distribution.

5.3. Handling of Dropouts or Missing Data

Rules for handling dropouts or missing data are listed by type of analysis alphabetically. Unless otherwise specified, observed data will be used and missing data will not be imputed or carried forward.

General rules for imputing dates related to adverse events (AEs) or concomitant therapy:

- Onset date of an AE or start date of a concomitant therapy:
 - if only the day is missing, the date will be set to:
 - the first day of the month that the event occurred, if the onset year-month (yyyy-mm) is after the yyyy-mm of first study treatment
 - the day of the first study treatment, if the onset yyyy-mm is the same as yyyy-mm of the first study treatment
 - if both the day and month are missing, the complete date will be set to:
 - January 1 of the year of onset, if the onset year is after the year of the first study treatment
 - the date of the first dose, if the onset year is the same as the year of the first study treatment
- Resolution date of an AE or end date of a concomitant therapy:
 - If only the day is missing, the date will be set to the last day of the month of the occurrence, or to the date of death if the patient died in the same month.
 - If both the day and month are missing, the date will be set to 31 December of the year of occurrence.

If a date is completely missing, then the AE will be considered treatment emergent. In case of additional therapies, the therapy will be considered concomitant.

General rule for imputing other dates: If a date variable is needed for an analysis, use the following general rule to impute the incomplete date:

- If the date has no missing year and month but the day is missing, then assign Day 1 to the day.
- If the date has no missing year, but has missing month, then assign January to the month.

However, after imputation, check if the imputed date is logically consistent with other relevant date variable(s) and make the appropriate correction if necessary. For example, if a visit start date was 10 May 2019 and a tumor assessment date was xx May 2019 (missing day) but it was known that it occurred after that visit, then after imputation, the tumor assessment date became 01 May 2019. In this case, the imputed tumor assessment date should be compared to the visit start date and then corrected to be the visit start date, 10 May 2019.

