8.3.1. Time Period and Frequency for Collecting AE and SAE Information

Although all AEs after signing the ICF are recorded by the site in the CRF/electronic data entry, SAE reporting to Lilly begins after the patient has signed the ICF and has received study drug. However, if an SAE occurs after signing the ICF, but prior to receiving LY3435151, it needs to be reported ONLY if it is considered reasonably possibly related to study procedures.

Medical occurrences that begin before the start of study intervention but after obtaining informed consent will be recorded on the AE CRF.

All SAEs will be recorded and reported to the sponsor or designee immediately and under no circumstance should this exceed 24 hours. The investigator will submit any updated SAE data to the sponsor within 24 hours of it being available. Serious adverse events, including death, caused by disease progression should not be reported unless the investigator deems them to be possibly related to study treatment.

Investigators are not obligated to actively seek AE or SAE after conclusion of the study participation. However, if the investigator learns of any SAE, including a death, at any time after a participant has been discharged from the study, and he/she considers the event to be reasonably related to the study intervention or study participation, the investigator must promptly notify the sponsor.

Care will be taken not to introduce bias when detecting AEs and/or SAEs. Open-ended and nonleading verbal questioning of the participant and/or legal guardian is the preferred method to inquire about AE occurrences.

Refer to the SoA (Section 1.3) for the timing of AE/SAE collection.

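### SAP 5.3 resolves incomplete AE onset dates toward first dose without using a known resolution date, so an AE documented as over before dosing can be counted as a TEAE

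*SAP*

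**What the plan says.** SAP 5.3 gives three rules that decide the treatment-emergent status of an AE with an incomplete onset date:

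- Day missing, onset in the first-dose month: onset becomes "the day of the first study treatment, if the onset yyyy-mm is the same as yyyy-mm of the first study treatment".
- Day and month missing, onset in the first-dose year: onset becomes "the date of the first dose, if the onset year is the same as the year of the first study treatment".
- No date at all: "If a date is completely missing, then the AE will be considered treatment emergent". I read this as referring to the onset date.

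Resolution dates have their own imputation. For a missing day, "If only the day is missing, the date will be set to the last day of the month of the occurrence", or the date of death if the patient died in that month. The onset rules do not refer to the resolution date.

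The section then starts a new block: "General rule for imputing other dates: If a date variable is needed for an analysis, use the following general rule to impute the incomplete date". After that block comes an instruction to "check if the imputed date is logically consistent with other relevant date variable(s) and make the appropriate correction if necessary", illustrated with a tumor assessment date.

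SAP 5.4.7 defines a TEAE as an event that first occurs or worsens between first dose and 30 days after last dose, plus related SAEs reported later. Protocol 8.3.1 puts pre-dose events in the same data: "Medical occurrences that begin before the start of study intervention but after obtaining informed consent will be recorded on the AE CRF".

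**The concern.** Dating an uncertain onset to first dose is sensible when the timing really is unknown. It is not sensible when the record already shows that the event ended before the patient was dosed. Such an event cannot have first occurred or worsened on treatment, yet the onset rules do not allow for it.

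Pre-dose events are to be expected here. Under the baseline schedule in Protocol 1.3, consent can be up to 28 days before Cycle 1 Day 1, and a pre-treatment biopsy is mandatory. Procedure complications and tumour symptoms from that window go on the AE form.

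TEAEs are among the primary safety endpoints in both phases (Protocol 3), and SAP 5.4 summarizes Phase 1a by dose level. From Cohort A2 on, a cohort may have as few as three evaluable patients, so one patient with a misdated event is 1/3 = 33% of a cohort of that size. What is at stake is the accuracy of the descriptive TEAE tables, not a dose decision.

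**Working it through.** The plan states no figure on this point. The check applies the rules to hypothetical cases and then asks how often a pre-dose onset could meet them.

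**1. The rules applied.** Assume first dose on 20 May 2019 and, where the event resolved, a documented resolution on 10 May 2019.

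| Onset as recorded | Resolution | Result under the AE onset rules | TEAE? | Would the consistency check catch it, if it covers AEs? |
|---|---|---|---|---|
| xx May 2019 | 10 May 2019 | 20 May 2019, 10 days after resolution | Yes | Yes, onset is after resolution |
| xx-xxx-2019 | 10 May 2019 | 20 May 2019, 10 days after resolution | Yes | Yes, onset is after resolution |
| completely missing | 10 May 2019 | status assigned, no date imputed | Yes | No, there is no imputed date to test |
| xx May 2019 | ongoing | 20 May 2019 | Yes | Nothing to catch; the default is reasonable |

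The first three rows conflict with SAP 5.4.7, because an event that ended on 10 May cannot have begun or worsened on or after 20 May. The first two depend on how far the consistency check reaches. The third fails on either reading.

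**2. A limit on the affected set.** A resolution in the first-dose month with its day missing is imputed to the last day of that month, so it never falls before first dose. Such an AE has no documented pre-dose end and properly stays treatment emergent. The problem needs both an incomplete onset and an end date known to precede dosing.

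**3. How often a pre-dose onset shares the first-dose month or year.** Assume a pre-dose window of 28 days (the consent limit) and first-dose days spread evenly.

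- In a 30-day month, an onset L days before dosing shares the month with probability (30 − L)/30. The mean of L over 1 to 28 is 14.5, so the average is (30 − 14.5)/30 = 0.517.
- Counting actual calendar days gives 0.523 for 2019 and 0.525 for 2020. The share in the same calendar year is 0.960 in both.
- If the events fall only in the last 14 days, the mean of L is 7.5 and the share is (30 − 7.5)/30 = 0.75.

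These shares show only that the same-month and same-year conditions are commonly met. They do not estimate misclassification, which also needs the date to be incomplete and the event to have resolved before dosing. The documents give neither frequency, so the effect on any TEAE rate cannot be computed.

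**4. With the resolution date used.** If a documented end before first dose means not treatment emergent, the first three rows change from TEAE to non-TEAE. The ongoing event in the fourth row stays a TEAE.

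**The case against.** **The consistency check already handles it.** An onset imputed after the event's own resolution is just the kind of conflict the check is meant to find. Its example is only an example, and nothing says AE dates are exempt. This is a fair reading, and on it both partial-date cases are corrected. It is not the only reading: the check follows the rule for other dates, after the AE rules are complete. It also tests an imputed date, so it does not touch the completely missing case. The general data review in Protocol 10.1.5 may prompt a query that recovers the date. However, the conflict between onset and resolution exists only after imputation, not in the reported data.

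**The TEAE definition governs.** Imputation supplies a date and does not redefine a TEAE. That is right in principle, but a program would apply the definition to the imputed onset, and the completely missing rule assigns the status directly.

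**The default is conservative.** It can add TEAEs but cannot hide toxicity. This stands wherever timing is unknown, and the fix keeps it there. It gives no reason to override a documented pre-dose end date.

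**Stronger readings do not hold.** A reader might infer that any AE with a missing date is called treatment emergent. The SAP says so only for a completely missing date; partial dates follow separate rules. A reader might also infer that screening events in general become TEAEs. Only those with incomplete onset dates can. Nor is dose escalation shown to be at risk: Protocol 4.1.1.1 makes DLTs the main safety criterion, and the DLT definition excludes toxicity clearly due to the disease or another cause.

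**Conclusion.** The point holds in a narrow form. Applied as written, the AE onset rules in SAP 5.3 can turn an event documented as resolved before dosing into a TEAE, against SAP 5.4.7. For partial onset dates this depends on whether the closing consistency check covers AEs, which the text leaves unclear. For a completely missing onset with a known pre-dose end date, it holds on either reading.

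The direction is known: the error can only add TEAEs. The size is not, because the documents do not say how many AEs will have incomplete dates. That the number is small is a judgement, not a figure from the plan. The conclusion assumes that the rules are programmed as written. It is a stated rule that gives a wrong result in identifiable cases, and the matter is minor.

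**What to change.** Add two statements to the AE rules in SAP 5.3:

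1. The check of imputed dates against other relevant dates also applies to AE and concomitant-therapy dates.
2. An AE whose documented end date is before the first dose is not treatment emergent, including when its onset date is completely missing. An AE with an unknown end date remains treatment emergent.

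The cost is a couple of sentences and minor programming. No new data are needed, and the conservative default is kept wherever timing is uncertain.

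As separate tidying that does not affect TEAE status: for resolution dates, SAP 5.3 says "If both the day and month are missing, the date will be set to 31 December of the year of occurrence", without the limit at death that the missing-day rule has. The same limit should apply, so that an imputed resolution cannot follow the patient's death.
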